**Table 2: Data Display for Safety**

Column Text Display	Description	Display Order
<=800mg	SRA737 daily total dose <= 800 mg	1
>800mg	SRA737 daily total dose > 800 mg, including BID dosing frequency	2
Overall	All subjects in the population	3

## 9.2.2. Reporting Conventions

The general programming considerations for tables, listings, and figures (TLFs) are provided in [Section 15](#). Actual formats and layouts may be altered slightly to accommodate actual data or statistics. Minor format changes will not require updates to the SAP. The TLF numbering and general content follow the ICH E3 guidelines.

In general, continuous variables will be summarized to include the population sample size (N), number of subjects with available data (n), arithmetic mean, standard deviation, median, minimum, Q1, Q3 and maximum values. Categorical variables will be summarized by the population size (N), number of subjects in each category, and the percentage of subjects in each category. A missing category will be added as the last category if appropriate.

The data analyses will be conducted using the SAS® System (SAS Institute Inc., Cary, NC) version 9.4 or above. The eClinical Solutions' standard operating procedures will be followed for the validation of all SAS programs and outputs.

## 9.2.3. Early Withdrawal and Missing Data

All subjects who withdrew early from the study will be included in the reporting if they meet the definition of the analysis population specified in [Section 8](#), regardless whether they were replaced for the purpose of DLT assessment.

In general, missing data will not be imputed and only observed values will be analyzed except for the data mentioned below.

If the date of diagnosis on the cancer diagnosis CRF page is partially missing, it will be imputed using the following rules for the purpose of calculating “Time Since Initial Diagnosis” summary.

- If only the day part is missing, day 15 will be used for imputation
- If both day and month parts are missing, July 1st will be used for imputation

If the relationship of an AE record is missing the AE will be considered “Related” to the study treatment for reporting purpose. If the Common Terminology Criteria for Adverse Events (CTCAE) grade of an AE is missing every effort should be made to acquire the information from the investigator. Grade 3 will be assigned to a missing grade for reporting purposes.

In general, missing or partial dates will not be imputed except for AE or medication start and end date.

The general imputation rules of partial missing date for both AE and concomitant medication are detailed below:

### For AE or medication start date

If the year portion is missing no imputation will be performed.

If the day portion is missing, the following rules will be implemented:

- Impute with first day of the month if the year and month of the start date is not equal to the year and month of the first study treatment (including PK dose)
- Impute with date of first study treatment if the year and month of the start date is the same as the date of the first study treatment (including PK dose)

If the month portion is missing, the following rules will be implemented:

- Impute with first day of the year if the year of the start date is not equal to the year of the first study treatment (including PK dose)
- Impute with date of first study treatment if the year of the start date is the same as the date of the first study treatment (including PK dose)

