10.2 EVALUATING AND RECORDING ADVERSE EVENTS

10.2.1 *SCREENING FAILURES*

For subjects who fail screening, SAEs must be reported to the Sponsor or Sponsor designee's Pharmacovigilance Department from the date of consent until the date the subject is confirmed as ineligible.

10.2.2 *DOCUMENTATION OF ADVERSE EVENTS*

For eligible subjects, SAE collection and monitoring will commence at the time the subject gives their written consent to participate in the trial, while AE collection and monitoring will commence at the time the subject receives their first dose of SRA737. SAE and AE collection and monitoring will continue until 30 days after the last administration of SRA737.

Should an investigator become aware of any drug-related SAEs after this 30-day period, these must also be reported to the sponsor or sponsor's designee within the expedited timelines in Section 10.3.

10.2.3 *MONITORING AND FOLLOW-UP OF AES AND SAEs*

All subjects will be monitored for AEs from the start of treatment through 30 after the last dose of study therapy. Additionally, monthly follow up is required for all SAEs and for those AEs considered drug related (highly probable, probable or possible) and present at the Safety Follow-up visit. Monthly follow-up will continue until the event resolves, returns to baseline, stabilizes, or the subject discontinues from study.

After a study participant's completion or discontinuation from the study treatment, the investigator remains responsible to follow (through an appropriate health care option) all SAE and any AEs that have been assessed as related to the IMP. Events will be followed for outcome (resolution, with or without sequelae; stabilization of the event in those cases where the condition is expected to be chronic; or death).

The reporting period for SAEs that the investigator considers to be related to a study procedure begins at the time the subject signs the informed consent document. Any SAE that occurs outside the time period specified above for AE monitoring (ie, through 30 days after the last dose of study therapy) that the investigator considers to be possibly, probably, or definitely related to study drug must be reported (refer to Section 10.1.2).

Follow-up information relating to an SAE must be reported to the Sponsor designee's Pharmacovigilance Department within 24 hours of site staff becoming aware of the new information.

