#### For AE or medication end date

If the year portion is missing no imputation will be done.

If the day or month portion is missing:

- Impute with the last day of the month (or of the year). If the imputed date is later than the date of death, the death date will be used to impute the end date.

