## 10.5. Prior and Concomitant Medication

Prior and concomitant medications will be summarized for the safety evaluable population. Medications will be coded using the World Health Organization (WHO) Drug B2-Sept 2016 version. These medications will be further classified as follows.

- Prior medication is defined as those medications that started prior to the study treatment (collected within 28 days prior to the first dose). If medications started prior to the study treatment and were ongoing after the study treatment, they will be considered as both prior and concomitant medications.
- Concomitant medication is defined as those taken on or after the study treatment. If medications started prior to the study treatment and were ongoing after the study treatment, those medication will be considered as concomitant medication as well.

If a medication's start date is completely missing, it will be counted in both prior and concomitant summaries. The number and percentage of subjects taking prior and concomitant medications will be summarized by Anatomical Therapeutic Chemical (ATC) Levels 2 and preferred terms (standardized drug name) by descending frequency based on all the subjects in the population.

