### 12.2. Adverse Events

Adverse events will be coded using MedDRA version 19.1.

An AE will be considered a treatment emergent adverse event (TEAE) if it begins or worsens in severity after the first dose of study treatment (including the dose for PK purpose). Partial AE

start dates will be imputed as detailed in [Section 9.2.3](#). If an AE start date is completely missing it will be considered a TEAE.

Summary tables will be based on TEAEs. The incidence of TEAEs will be presented using counts and percentages of subjects with TEAEs and tabulated by SOC and PT. SOC will be sorted in descending frequency and PT within SOC will be sorted by descending frequency based on the incidence of all subjects in the population. If a subject has multiple occurrences (start and stop) of an event associated with a specific SOC or PT within a SOC, a subject will only be counted once in the incidence count for the SOC or PT within SOC respectively.

An overall summary table of AEs will be presented detailing the number and percentage of subjects for the following categories. One additional overall summary of AEs by disease categories instead of Cycle 1 total dose with the same AE categories below will also be presented.

- At least one TEAE;
- At least one Treatment-Related TEAE;
- At least one Grade  $\geq 3$  TEAE
- At least one Grade  $\geq 3$  Treatment-Related TEAE;
- At least one Serious TEAE;
- At least one Serious Treatment-Related TEAE;
- At least one Serious AE Occurred Prior to First Dose
- At least one TEAE leading to Treatment Withdrawn;
- At least one Treatment-Related TEAE leading to Treatment Withdrawn;

Except for all TEAEs which will be summarized by SOC and PT, the incidence of all other TEAEs by PT will be presented for the following in descending frequency based on the incidence of all subjects in the population.

- All TEAEs;
- Treatment-related TEAEs;
- TEAEs with Grade  $\geq 3$ ;
- Treatment-related TEAEs with Grade  $\geq 3$ ;
- Serious TEAEs;

- Treatment-related serious TEAEs;
- Serious AEs Occurred Prior to First Dose
- TEAEs leading to Treatment Withdrawn
- Treatment-related TEAEs leading to Treatment Withdrawn

A Treatment related AE is defined as an AE for which the investigator classifies the relationship to study treatment as being “Highly probable”, “Probable”, or “Possible” on Adverse Event eCRF. Missing relationship and toxicity grade will be imputed per [Section 9.2.3](#).

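### SAP 9.2.3 moves some partial start dates to the first-dose date without checking the stop date, so a serious event or medication that ended before dosing can lose its pre-treatment status

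*SAP*

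**What the plan says.** SAP 9.2.3 gives four rules for a partial AE or medication start date. First treatment includes the single PK dose.

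- Day missing, same month and year as first treatment: "Impute with date of first study treatment if the year and month of the start date is the same".
- Day missing, another month: "Impute with first day of the month if the year and month of the start date is not equal to the year and month" of first treatment.
- Month missing, same year: "Impute with date of first study treatment if the year of the start date is the same as the date of the first study treatment".
- Month missing, another year: "Impute with first day of the year if the year of the start date is not equal to the year of the first study treatment".

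The end-date rule reads "Impute with the last day of the month (or of the year). If the imputed date is later than the date of death", in which case the death date is used. No rule compares the start with the stop.

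SAP 12.2 uses the imputed start to decide whether an event is treatment-emergent, which requires onset or worsening after the first dose. For AEs with no start date it adds: "If an AE start date is completely missing it will be considered a TEAE". SAP 10.5 calls a medication prior if it started before study treatment, and concomitant if it was taken on or after study treatment. For medications with no start date it says: "If a medication's start date is completely missing, it will be counted in both prior and concomitant summaries".

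Protocol 10.2.2 states that "SAE collection and monitoring will commence at the time the subject gives their written consent to participate in the trial", whereas other AEs are collected only from the first dose. SAP 12.2 and Table 14.3.2.9 report serious events before first dose separately from serious TEAEs.

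**The concern.** Placing an onset of uncertain timing at the first dose is a common cautious choice. It is no longer cautious when a recorded stop date shows that the event was over before any drug was given. The rule then overrides known data and produces a record that ends before it starts.

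Adverse events are a primary endpoint (Protocol 3.1.1, SAP 4.1), and safety is displayed in two dose columns (SAP Table 2), so even one or two misplaced SAEs could be noticeable. SAP 9.2.3 also sets a missing relationship to related and a missing grade to Grade 3. A pre-dose SAE record that lacked those fields too could therefore be reported as a treatment-related, Grade 3 or higher, serious TEAE.

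**Working it through.** The SAP states no figure to reproduce. The check applies the four start-date rules literally to example records and then asks how many pre-dose starts the rules can move.

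**Can such records exist?** Yes. SAEs are collected from consent, and Protocol 7.1.1 sets no time limit on pre-screening consent, so weeks may pass between consent and dosing.

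**Example records.** Assume first dose on 20 March 2017. The last column is stop − imputed start + 1, in days.

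| Record | Recorded start | Recorded stop | Start after SAP 9.2.3 | Signed length |
|---|---|---|---|---|
| SAE A | March 2017, day unknown | 10 March 2017 | 20 March 2017 | 10 − 20 + 1 = −9 |
| SAE B | 2017, month unknown | 10 February 2017 | 20 March 2017 | −38 + 1 = −37 |
| SAE C | February 2017, day unknown | 10 March 2017 | 1 February 2017 | 37 + 1 = 38 |
| Medication D | March 2017, day unknown | 10 March 2017 | 20 March 2017 | −9 |
| Medication E | 2017, month unknown | 10 February 2017 | 20 March 2017 | −37 |
| Medication F | February 2017, day unknown | not needed | 1 February 2017 | starts before dosing |
| Medication G | 2015, month unknown | not needed | 1 January 2015 | starts before dosing |

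Records A, B, D and E ended before dosing but receive a start after their own end. Records C, F and G are placed before dosing, as they should be.

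**Where SAEs A and B are reported.** The imputed onset equals the first-dose date. SAP 12.2 says after the first dose and does not say whether the same day counts.

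- If it counts, A and B become serious TEAEs.
- If it does not, they are not TEAEs, and with a start on the first-dose date they are not before it either. They fall out of both sets of tables.

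Both outcomes are wrong. The duration formula in SAP 9.3.2 (later date − earlier date + 1) can also hide the fault: for A it gives 20 − 10 + 1 = 11 days, which looks plausible.

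**Where medications D and E are reported.** With a start on the first-dose date they did not start before treatment, so they are not prior. With a stop before dosing they were not taken on or after treatment, so read literally they may not be concomitant either. With no start date at all, each would have been counted as both.

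**How many pre-dose starts can be moved.** Assume first-dose days spread evenly over the 365 days of 2017.

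- *True starts uniform over the 28 days before dosing:* 365 × 28 = 10,220 pairs. For a first dose on day d of a month, the smaller of d − 1 and 28 pre-dose days fall in that month. This sums to 462 for a 31-day month, 434 for a 30-day month and 378 for February. The total is 7 × 462 + 4 × 434 + 378 = 5,348, or 52.3% moved if the day is missing. The pairs that cross the year boundary number 28 + 27 + … + 1 = 406, so (10,220 − 406) / 10,220 = 96.0% are moved if the month is missing.
- *True starts uniform over the previous 365 days:* 365 × 365 = 133,225 pairs. Same month: 7 × 465 + 4 × 435 + 378 = 5,373, or 4.0%. Same year: 0 + 1 + … + 364 = 66,430, or 49.9%.

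These shares count every pre-dose start that is moved, including events or medications still ongoing at first dose. Under each assumption they are therefore only an upper bound on the share that is moved and had also stopped before dosing.

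**The case against.** The strongest reply is that the AE route is narrow. It needs an SAE between consent and first dose, with an unknown start day, a known stop, and a subject who was still dosed. SAEs are reported within 24 hours, dates of occurrence must be recorded, and the eCRF is reconciled with the safety database (Protocol 10.3, 10.4) and queried (12.4). Medication start and stop dates are also required (Protocol 5.5.1). Counting the event as a TEAE overstates toxicity, in keeping with the other defaults in SAP 9.2.3, in an uncontrolled study whose statistics are only supportive (SAP 9.1.2). Listings show missing date parts as dashes (SAP 15.3.3), so a careful reader could find the record.

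All of this bears on frequency and consequence, and it stands there. It does not make the rule right: caution does not justify overriding a recorded stop date, and on the stricter reading of SAP 12.2 the SAE drops out of both tables, which is not conservative.

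Three stronger readings are tempting and are not supported.

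- A reader might infer that a partially dated medication can never be prior. Medications F and G show otherwise.
- A reader might infer that medications D and E become concomitant only, a shift in one fixed direction. SAP 10.5 defines concomitant by use on or after treatment, so that is not established. SAP 9.2.3 also introduces the rules as being for AEs and concomitant medications, which leaves their use for purely prior medications somewhat unclear.
- A reader might take 52% and 96% as the error rate. They rest on an assumed 28-day window, fall to 4% and 50% over a year, and ignore whether the record had stopped.

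**Conclusion.** The point holds in a limited form. For a day-missing start in the month of first treatment, or a month-missing start in that year, SAP 9.2.3 gives a wrong result whenever the stop is known to precede dosing. An SAE is either reported as a serious TEAE or lost from both the serious TEAE tables and Table 14.3.2.9. A medication loses its prior status, so partial information is treated worse than none. The completely missing rule for AEs has the same gap: a stop before dosing does not prevent treatment-emergent status.

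The AE effect is essentially limited to SAEs between consent and first dose. The number of affected records cannot be found from the documents and is probably small. This is a low-priority correction that is worth making because it costs little.

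**What to change.** Add to SAP 9.2.3: *If the recorded or imputed stop date is before first study treatment, do not impute the start to the first-treatment date. Use the earliest date consistent with the known parts (for SAEs, not before consent) and classify the record as pre-treatment: SAE, prior to first dose; medication, prior only.* The consent limit prevents a month-missing SAE from being set to 1 January, before SAE collection began.

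Apply the same stop-date check to completely missing starts in SAP 12.2 (AEs) and SAP 10.5 (medications).

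Do not instead count every same-month or same-year partial medication as both prior and concomitant, because that would put drugs begun on study into the prior table.

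The check is safe. The end-date rule takes the latest possible day, limited only by death, so an imputed stop before first dose shows that the event had ended by then.

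The cost is the added rule text, two cross-references and one condition in the imputation program. No new data are needed.

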#### For AE or medication end date

If the year portion is missing no imputation will be done.

If the day or month portion is missing:

- Impute with the last day of the month (or of the year). If the imputed date is later than the date of death, the death date will be used to impute the end date.

#### **9.2.4. Analysis Visiting Windows**

No analysis visit window will be defined for safety data or efficacy data except for the tumor marker data. All post-baseline radiological disease assessments will be used for analyses purpose. Nominal clinical visits that are defined in the protocol “Schedule of Event” will be used for summary of safety endpoints. Any unscheduled safety data will not be included in the by-visit summary and will be included in the listings.

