5.5.1.2 Palliative Radiotherapy

Palliative radiotherapy may be given concomitantly for the control of bone pain or other symptoms. Irradiated lesions will not be evaluable for response.

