7.3 SAFETY FOLLOW-UP (SFU) VISIT

If a subject discontinues the IMP for any reason, a Safety Follow-up (SFU) visit should be completed. Evaluations at the SFU visit should be performed 30 days \pm 7 days after the last dose of SRA737. If the subject begins a new anticancer treatment within 30 days of the last administration of the IMP, the SFU visit should be performed prior to initiation of the new anticancer treatment, if possible. The following investigations should be performed wherever possible:

- Assessment of AEs (also see Section 7.2.1) and review of concomitant medications
 - Monthly follow up is required for all SAEs and for those AEs considered drug related (highly probable, probable or possible) and present at the SFU visit. Monthly follow-up will continue until the event resolves, returns to baseline, stabilizes, or the subject discontinues from study.
- A symptom-directed physical examination including WHO performance status, temperature, pulse rate, seated BP and weight
- Laboratory tests (blood/urine samples):
 - Hematology tests: CBC with differential count detailed in Section 7.1.2
 - Biochemistry tests: detailed in Section 7.1.2
 - Troponin T or Troponin I: detailed in Section 7.1.2
 - Urinalysis: detailed in Section 7.1.2
 - Blood sample for additional exploratory analyses (such as mutational burden)
 - ctDNA for exploratory analyses (from a subset of up to 33 subjects)
 - CTCs for mCRPC subjects only unless PD was previously documented
 - Serum tumor marker (if applicable, eg, CA-125 for ovarian cancer, PSA for prostate cancer, CEA for colorectal cancer, CA19-9 for pancreatic cancer, AFP for liver and other cancers, and others as clinically indicated must be repeated) unless PD was previously documented
 - Urine or serum pregnancy test
- ECG (locally-read)
- ECHO

- Clinical (if applicable) and radiological assessment of disease, unless PD was indicated on a previous study scan or radiological disease assessments were conducted within the past 6 weeks.
- Compliance: the subject's most recent diary card must be collected and checked for completeness and compliance in taking SRA737.

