2.4. Evaluation of best overall response

The best overall response is the best response recorded from the start of the study treatment until the end of treatment. Should a response not be documented until after the end of therapy in this trial, post-treatment assessments may be considered in the determination of best overall response as long as no alternative anti-cancer therapy has been given. The subject's best overall response assignment will depend on the findings of both target and non-target disease and will also take into consideration the appearance of new lesions.

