### 11.1. Overall Response

#### 11.1.1. Overall Response Rate

Overall response rate will be assessed by the investigator per RECIST criteria version 1.1. Partial or complete response should be confirmed by a repeat tumor imaging assessment not less than 4 weeks from the date the response was first documented. The confirmed responses will be derived based on the overall responses by timepoint using the logics below:

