**Table 3: Confirmed Response per RECIST 1.1**

Initial Response	Subsequent Timepoint	Confirmed Response
Complete Response (CR)	CR at least 4 weeks after initial CR (or consecutive CRs with at most one NE in between with the last CR at least 4 weeks after initial CR)	CR
	CR less than 4 weeks	SD

Initial Response	Subsequent Timepoint	Confirmed Response
	PD or Not Evaluable (NE) or no subsequent assessment	SD if CR is at least 6 weeks from Cycle 1 Day 1, otherwise PD or NE
Partial Response (PR)	PR/CR at least 4 weeks after initial PR (or consecutive PRs/CRs with NEs in between with the last PR/CR at least 4 weeks after initial PR)	PR
	PR/CR less than 4 weeks, or SD	SD
	PD or NE or no subsequent assessment	SD if PR is at least 6 weeks from Cycle 1 Day 1, otherwise PD or NE
Stable Disease (SD)	PD or NE, SD, or no subsequent assessment	SD if SD is at least 6 weeks from Cycle 1 Day 1, otherwise PD or NE
Progressive Disease (PD)	Any assessment or no subsequent assessment	PD

The best overall confirmed response will be the best confirmed response from the above following the order of CR > PR > SD > PD > NE

The best overall response will be summarized for the following endpoints with count and percentage:

- CR
- PR
- SD
- PD
- NE
- ORR (CR + PR) with 95% CI (Wilson method [1])
- DCR (CR + PR + SD) with 95% CI (Wilson method)

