### 11.1.5. Change in Target Tumor Size

At each timepoint of imaging assessment the sum of the longest diameter of all the target lesions are derived. The change and percentage change from baseline to the post-baseline nadir will be summarized. A waterfall plot of best percent change from baseline (from baseline to nadir) by tumor type cohorts will be provided.

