## 11.2. Time to Progression (TTP)

Time to progression is defined as time from the Cycle 1 Day 1 to the earliest date of radiographic disease progression per RECIST 1.1. If a subject did not experience progressive disease, TTP is censored at the last imaging assessment. TTP will be analyzed using the Kaplan-Meier method. The output will include count and percentage of subjects with events or censored outcome including the type of event and censoring. Median TTP and 95% CI based on log-log

transformation will be provided. Landmark analyses at various timepoints may be carried out if of clinical interest. Kaplan-Meier plot supporting the table summary may also be generated.

In addition to TTP by RECIST 1.1 criteria based only on the radiographic assessments, a second definition of TTP which incorporates the clinical progression will be used. The clinical progression is based on the medical review of the reasons of treatment discontinuation or study continuation. If a subject is considered having clinical progression the date of treatment or study discontinuation will be used as date of clinical progression and the TTP is defined as time from Cycle 1 Day 1 to the earliest date of clinical or radiographic disease progression.

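### The SAP omits the protocol's limits on irradiated lesions and on scans after another anticancer therapy, so nadir change, the waterfall plot and DCR can include the effect of other treatment

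*SAP*

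**What the plan says.** Protocol 5.5.1.2 permits palliative radiotherapy during the trial for symptom control and adds: "Irradiated lesions will not be evaluable for response". Appendix 2, 2.4 covers responses first seen after treatment has ended: "post-treatment assessments may be considered in the determination of best overall response as long as no alternative anti-cancer therapy has been given". Appendix 2, 2.4.2 and Table 1 of that appendix make a time point with only some lesions assessed normally NE, although PD can still be called. In the schedule of events (7.6), footnote m is attached to the radiology cells for safety and long-term follow-up. It ends disease assessment at PD or at the start of subsequent anticancer therapy.

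SAP 9.2.4 states: "All post-baseline radiological disease assessments will be used for analyses purpose". SAP 11.1.5 states: "At each timepoint of imaging assessment the sum of the longest diameter of all the target lesions are derived"; the change to the post-baseline nadir then feeds Table 14.2.1.2 and the waterfall plot. SAP 11.1.1 states: "The confirmed responses will be derived based on the overall responses by timepoint using the logics below". The rows of Table 3 that follow depend only on response category and timing, and ORR and DCR come from that derivation. SAP 13 lists five changes from the protocol, and neither omission is among them.

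**The concern.** The protocol sets aside two kinds of tumor data because they may reflect a treatment other than SRA737. An analyst who follows the SAP literally would put both back. SAP 1 says the plan is meant to explain in detail how data will be handled, so silence here cannot safely be read as importing the protocol's limits.

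ORR and DCR are among the primary efficacy endpoints (Protocol 3.1.1), and the SAP places change in target tumor size under its Overall Response section. The expansion cohorts have about 20 subjects each and no control arm, so nothing in the design would expose shrinkage or disease control caused by radiotherapy or by the next drug.

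**Working it through.** **1. The plan's own figure.** Protocol 11.2.3 tabulates Wilson 95% intervals for n = 20:

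(p + z²/2n ± z√[p(1-p)/n + z²/4n²]) / (1 + z²/n), with z = 1.96.

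At 0/20 the upper limit is z²/(n + z²) = 3.84/23.84 = 0.161, as stated. All 21 rows reproduce to three decimals. No stated number is in dispute; the table only gives scale.

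**2. The texts side by side.**

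| Data | Protocol | SAP |
|---|---|---|
| Irradiated target lesion | Non-evaluable for response (5.5.1.2) | Stays in the target sum (11.1.5) |
| Scan after another anticancer therapy | Not usable for best overall response (Appendix 2, 2.4) | Used (9.2.4); no cut-off in Table 3 |
| Declared as a change | n/a | No (13) |

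**3. Irradiated lesion, nadir and waterfall.** Protocol 9.2.2 requires every lesion measured at baseline to be measured at each later assessment, so an irradiated lesion's measurements will be in the database. Lesion sizes below are assumed.

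- Baseline sum: 40 + 30 + 30 = 100 mm.
- Follow-up, with only the 40 mm lesion irradiated and now 10 mm: 10 + 30 + 30 = 70 mm.
- Plotted change: (70 - 100)/100 = -30%, the PR threshold in Appendix 2, 2.3.1.
- Unirradiated lesions: (60 - 60)/60 = 0%.

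More generally, take k equal target lesions, one irradiated and shrinking by a fraction s, the rest unchanged. The sum changes by -s/k.

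| s | k = 2 | k = 3 |
|---|---|---|
| 60% | -30% | -20% |
| 80% | -40% | -27% |
| 100% | -50% | -33% |

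Reaching -30% needs s of at least 0.3k: 60% with two lesions and 90% with three. With five equal lesions it would need 150%, so one lesion cannot do it. The nadir is a minimum with no confirmation rule, so one low reading is enough.

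**4. Scan after new therapy, DCR.** Footnote m should prevent such a scan, but one can arise off schedule.

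- Protocol 7.3 says "the SFU visit should be performed prior to initiation of the new anticancer treatment, if possible", and its own scan line exempts only earlier PD or a scan in the past 6 weeks.
- Protocol 9.2.2 asks for re-evaluation when treatment stops for reasons other than PD, and 5.6 lists starting new anticancer therapy as a reason for stopping.

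If the scan reads SD at least 6 weeks after Cycle 1 Day 1, in a subject with no earlier qualifying SD or better, Table 3 returns SD and DCR gains one. From an assumed 6/20 = 30% (14.5% to 51.9%), DCR becomes 7/20 = 35% (18.1% to 56.7%). Each such subject adds 1/20 = 5 percentage points.

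**5. Confirmed ORR.** Table 3 requires a CR or PR to be repeated at least 4 weeks later, and it works from the investigator's time-point responses. One stray scan cannot create a confirmed response. Lasting radiotherapy shrinkage could do so only if the investigator kept the lesion in the time-point call despite 5.5.1.2. No shift in ORR follows from the documents.

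**The case against.** The sentence in SAP 9.2.4 sits in a section on visit windows, and its natural purpose is to say that unscheduled scans count. That is a fair reading, but no other SAP text supplies the two exclusions.

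Scans after new therapy should hardly exist. Footnote m stops them, and Protocol 5.5.2 bars other anticancer therapy on trial. A scan taken at discontinuation would precede the safety follow-up visit (30 ± 7 days after the last dose) by about 23 to 37 days, so the 6-week exemption in 7.3 would usually remove the follow-up scan. This stands as to frequency. Footnote m governs collection, however, and does not tell the analyst what to do with a scan that was taken.

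Investigators are bound by 5.5.1.2, and Appendix 2, 2.4.2 already makes partly assessed time points NE. This largely protects ORR and DCR from the radiotherapy route. It does not protect SAP 11.1.5, which works from the lesion measurements themselves.

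Many irradiated sites will be bone lesions, which Appendix 2, 1.1.2 counts as measurable only with a qualifying soft-tissue component. This also stands and lowers the likely number.

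A reader might infer that the time-to-event rules breach the protocol too, since in SAP 11.2 "TTP is censored at the last imaging assessment" and Table 4 has no row for new therapy. The documents do not support that. The limit in Appendix 2, 2.4 concerns best overall response, and Protocol 11.2.3 leaves PFS censoring to the SAP. Barring later scans only as censoring dates would also be lopsided, because progression after new therapy would still count as an event.

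**Conclusion.** The point holds in a limited form. The protocol sets two limits on tumor data, the SAP carries neither, and section 13 does not declare the departure. The clearest exposure is the nadir table and waterfall plot, where radiotherapy alone can give a PR-sized value with no change in the other lesions. The lesser exposure is DCR, at 5 percentage points per affected subject in a cohort of 20.

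A reader might go further and infer that confirmed ORR is inflated, so that a cohort moves from 0/20 (upper limit 16.1%) to 1/20 (0.9% to 23.6%) and the protocol's statement that 0/20 excludes an ORR of 16% is lost. That would assume the extra response; the confirmation rule and the investigator-based calls mean it is not shown. Nor do the documents show that other treatment will routinely be credited to SRA737, only that it can be.

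The conclusion assumes that the SAP is followed as written. The lesion sizes and the 6/20 starting point are illustrations, and the documents give no count of affected subjects.

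**What to change.** In SAP 9.2.4, 11.1.1 and 11.1.5, state:

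- (a) Scans on or after the start of any alternative anticancer therapy are excluded from best overall response, ORR, DCR, change to nadir and the waterfall plot. Palliative radiotherapy permitted by Protocol 5.5.1.2 falls under (b).
- (b) From the date a target lesion is irradiated, the target sum is missing for nadir and waterfall, and the time point is NE unless PD is met, consistent with Appendix 2, 2.4.2.

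List the affected subjects. The sum should be set to missing rather than recomputed without the irradiated lesion: in the example, 60 mm against an unchanged baseline of 100 mm would show -40%, further from the 0% seen in the unirradiated lesions. Leave the TTP, PFS and DOR censoring rules as they are.

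The cost is SAP wording and some programming. A few time points become NE, and ORR or DCR may be slightly lower. The first subsequent therapy is collected (Protocol 7.4); that its start date is available is an assumption. Irradiated sites must also be matched to target lesions. The documents do not show a lesion-level link, so this is assumed possible from the recorded concomitant treatment.
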